### **5.6 End of Study Definition**

The study end date is deemed to be the date of the last data capture. Reasonable attempts will be made to contact non-responders. The CI has the right at any time to terminate the study for clinical or administrative reasons. The end of the study will be reported to the Sponsor and REC within the required timeframe if the study is terminated prematurely. Investigators will inform patients of any premature termination of the study. Following the end of the study a summary report of the study will be provided to the REC within the required timeframe.

## **6. Assessment of Safety**

### **6.1 Safety outcomes**

Whilst we do not anticipate any adverse events or safety risks for patients or members of the research team from participation in this study, it is possible that patients engaging with this study may be experiencing psychological distress. With each online or paper questionnaire, information will be provided about ICUsteps, a national support group network who are aware of and support this study. Participants will also be encouraged to engage with their local ICU follow up clinic if available locally (e.g. at 3 months) or contact their GP if they feel they need additional support.

### **6.2 Ethics Reporting**

Approval from a Research & Ethics Committee (REC) will be sought. The REC will be informed about any changes according to the official National Research Ethics System regulations. Local site investigators will be responsible for ensuring appropriate approvals from local research committees, audit committees or R&D centres are obtained as required to ensure compliance with local policies.

### **6.3 Data Safety and Monitoring Board**

This is a longitudinal study with no change in clinical practice. A data safety and monitoring board will not be established.

### **6.4 Ethics & Regulatory Approvals**

The study will be submitted centrally for consideration by a NRES approved Research Ethics Committee and by the HRA, as well as local RD&I approvals.

## 7. Data Handling

### 7.1 Confidentiality

- All local sites will maintain an enrolment and recruitment log, which will include patient hospital identification number, name and contact details and will be held in a locked office at the local site. Only members of the local study team will have access to this list.
- Patient confidentiality will only be breached if a participant discloses information which may indicate harm to themselves or others. We will take every opportunity to discuss any possible breaches of confidentiality with patients before informing any appropriate agencies (e.g. patient's registered general practitioner).
- All enrolled patients will be allocated a unique study number which will be used for referencing data recorded and entered into the REDCap database. This study number will be used as the patient identifier to link to clinical variables.
- To avoid the possibility of identifying patients via their postcode, study members will be looking up the deprivation index using government data specific to England, Northern Ireland, Scotland and Wales. This deprivation index will then be entered into the REDCap database. The patient's postcode will be found in the patient's records and not be recorded in the REDCap database.
- All online questionnaires, and online generated data, will be held in a secure server. If necessary, paper copies of questionnaire results will be printed and stored at local sites. Printed questionnaires will be entered into the REDCap database by local study team members, so as to merge all data together for analysis.
- All paper documents (including participants' written consent forms and returned paper questionnaires) will be held securely at the study site in a restricted access area, in line with data protection regulations.
- The Chief Investigator will act as 'Custodian' for all data collected.
- No patient identifiable details will be included in the published study reports.
- No information regarding the study will be released to or by a third party without the prior written consent of the sponsoring institution.
- Representatives of the sponsoring institute may inspect all documents and records required to be maintained by the investigators.

### 7.2 Case Report Form

Data will be recorded via individual electronic case report forms (eCRF) through the REDCap (<https://www.project-redcap.org/>) online database tool. Local investigators will be responsible for

individual hospital data input into REDCap. Local investigators are responsible for data collection, input and accuracy.

### **7.3 Record Retention and Archiving**

All research and relevant documents will be stored confidentially and securely for 10 years following the end of the study as per the Sponsor's standard operating procedure on research archiving. The members of the study management team will have access to stored data. Upon request, investigators can get access to data from their own site.

### **7.4 Compliance**

The study will be conducted in compliance with the principles of the Declaration of Helsinki (1996), and in accordance with all applicable regulatory requirements including but not limited to the Research Governance Framework, Trust and Research Office policies and procedures and any subsequent amendments. Personal patient data will be pseudo-anonymised and will be held in compliance with EU General Data Protection Regulations (GDPR) and the UK Data Protection Act (2018).

### **7.5 Clinical Governance**

The study may be selected for audit by any method listed below:

- The project may be identified via the risk assessment process.
- An individual investigator or department may request an audit.
- A project may be identified via an allegation of research misconduct or fraud or a suspected breach of regulations.
- Projects may be selected at random. The Department of Health states that Trusts should be auditing a minimum of 10% of all research projects.
- Projects may be randomly selected for audit by an external organisation.
- Internal audits will be conducted by a sponsor's representative

### **7.6 Non-Compliance**

Non-compliances may be captured from a variety of different sources including eCRFs, communications and updates. The sponsor will maintain a log of the non-compliances to ascertain if there are any trends developing which require to be escalated. The sponsor will assess the non-compliances and action a timeframe in which they need to be dealt with. Each action will be given a different timeframe dependent on the severity. If the actions are not dealt with accordingly, the R&D team will agree to an appropriate action, including an on-site audit. All protocol and GCP deviations will be reported to the Sponsor and

serious non-compliance will be reported to REC, in line with the SAE/protocol deviation SOPs of the Sponsor.

### ***7.7 Protocol Amendments***

Any changes in research activity will be reviewed and approved by the Chief Investigator and submitted in writing to the appropriate REC and local research site for approval prior to being included in an amended protocol.

### ***7.8 Study Management***

The Co-Chief Investigators, [name] and [name], will have managerial oversight of the project. The day-to-day management and data collection will be coordinated by the TRIC network, with junior doctors at each site performing patient identification, data collection and appropriate participant contact, in conjunction with allied health professionals working with the TRIC network. The analysis will be led by [name], with clinical input provided by the TRIC network.

## **8. Finance and Publication Policy**

### ***8.1 Finance***

Funding is provided by the Intensive Care Society and the Mersey School of Anaesthesia.

### ***8.2 Publication Policy***

It is planned to publish the study results, in mutual agreement with the investigator team, in a scientific journal and present the findings at international congresses. Publication of the results of the study as a whole is intended. Requirements for authorship will follow American Medical Association (AMA) guidance. Any publication will take account of the International Committee of Medical Journal Editors (ICMJE) relevant policies and guidelines. The study will also be registered in a public register in accordance with the recommendations of the ICMJE. Any published data will observe data protection legislation covering the study subject and investigators. Individual findings at individual study sites are known only to the responsible institution. A lay summary of the results will be made available to participants upon their request.

Publications or lectures presenting findings of the study (either as a whole or at individual investigation sites) must be approved by the chief investigator in advance, and the responsible institution reserves the

right to review and comment on such documentation before publication. Publication should include details of the sponsor and other major study contributors, but with no patient identifiable details.

## 10. Appendices

### Appendix 1: Information with regards to Safety Reporting in Non-CTIMP Research

[figure not shown]
	Who	When	How	To Whom
SAE	Chief Investigator	Report to sponsor within 24 hours of learning of the event  Report to the MREC within 15 days of learning of the event	SAE report form for non-CTIMPs, available from NRES website.	Sponsor and MREC
Urgent Safety Measures	Chief Investigator	Contact the sponsor and MREC immediately  Within 3 days	By phone  Substantial amendment form giving notice in writing setting out the reasons for the urgent safety measures and the plan for future action.	Main REC and sponsor  Main REC with a copy also sent to the sponsor. The MREC will acknowledge this within 30 days of receipt.
Progress Reports	Chief Investigator	Annually (starting 12 months after the date of favourable opinion)	Annual progress report form (non-CTIMPs) available from the NRES website	Main REC
Declaration of the conclusion or early termination of the study	Chief Investigator	Within 90 days (conclusion)  Within 15 days (early termination)  The end of study should be defined in the protocol	End of study declaration form available from the NRES website	Main REC with a copy to be sent to the sponsor

Summary of final Report	Chief Investigator	Within one year of conclusion of the research	No standard format However, the following Information should be included: Where the study has met its objectives, the main findings and arrangements for publication or dissemination including feedback to participants	Main REC with a copy to be sent to the sponsor
--------------------------------	--------------------	---	---	--

[figure not shown]
## Appendix 2: Study Flowchart

### Appendix 3a: Study Gantt Chart

### Appendix 3b: Interviews & Survey Gantt Chart

## **Appendix 7: Interview Guide**

Interviews will be arranged at a time convenient for the participant and will be conducted via telephone, an online secure platform (e.g. MS Teams or Zoom), or in person at the Royal Liverpool University Hospital, James Cook University Hospital or the participant's home, as per the participant's preference and current government guidance regarding lockdowns.

Closed questions are to be avoided as much as possible. To ensure that the research questions are addressed, a semi-structured approach should be used. Interruptions from the interview should be kept to a minimum, with the interviewer reflecting, prompting and summarising, with open or closed questions and probing where appropriate. Participants should be encouraged to speak about their specific experience.

Before the interview commences, ensure that the participant has read the information sheet. Questions and prompts below are resources on which the interviewer can draw and only relevant questions should be asked.

### **1. Introduction**

### **2. Reassurance of confidentiality**

Ensure the participant that their answers will be treated confidentially, and their interview will be anonymised before being analysed. Confidentiality will only be broken if they say something that indicates risk to themselves or others.

### **3. Clarification of research aims and the interview purpose**

### **4. Time for questions from the participant about the interview and/or information sheet**

Remind participants that the interview will be recorded.

### **5. Interview questions**

The format and sequencing will be guided by the patient's responses.

- What has your experience been since leaving intensive care?
- What psychological and/or physical symptoms have you experienced, including:
  - Difficulty concentrating
  - Breathlessness
  - Coughing
  - Difficulties sleeping
  - Nightmares
  - Pain
  - Weakness
  - Fatigue
  - Intrusive thoughts
  - Seeing insects
- Have your psychological and/or physical symptoms changed over the course of your recovery?
- If so, how?
- Do you think your physical symptoms (e.g. breathlessness, pain, weakness) have affected your mental well-being?
- How do you think that COVID-19 has affected your recovery, if at all?
- How have any of the following COVID-19 related factors influenced your recovery:
  - Restricted family/friend visiting whilst in hospital
  - Staff wearing PPE
  - Difficulty getting face to face appointments with your GP
  - Reminders about COVID-19 in the media.
  - Family support. Limits on family/friends visiting when at home because of lockdown. Or more family support because of furlough.
- What follow-up services have you been offered?
- Have you attended ICU follow-up clinic?
  - If no, why not?

- If yes, did you find it helpful and what services were offered as part of that (ICU doctor, physio, dietician, respiratory physician)
  
- Were you given a phone number to contact for advice?
- Did you use it?
  - If no, why not?
  
- Is there any other support that you would have liked to have been offered?
  
- Were you contacted to attend a follow-up clinic? Would you have preferred to have been contacted once you got home (at an earlier time point than being invited for follow-up clinic)?
- At what time frame would you have found that helpful?
  
- What support do you think you would have benefitted from?
  
- Did you feel you knew what to expect during your recovery?
- Were you given any information regarding what experiences to expect during your recovery e.g. timespan / symptoms?
  - If so what information was given?
  - Where you satisfied with the information given?
- Specifically - were you given information about ICU recovery / ICUsteps / locally available support services?

## **6. Close**

- Is there anything else you would like to share?

Thanks for taking part.

## Appendix 8: Survey of Intensive Care Follow-Up Services

Thank you very much for agreeing to provide the information included in this survey. We appreciate your contribution.

The COVID-19 pandemic has put significant strain on the NHS, not only in direct provision of acute care, but also on follow-up services. At the same time, patients who survive critical COVID-19 often suffer from long-term psychological sequelae, including anxiety, post traumatic distress syndrome and prolonged functional recovery ('long COVID'). In this survey we wish to evaluate the existing follow-up care provided by intensive care units within the UK to address the needs of patients after discharge from hospital.

### Instructions:

Please complete the questions in the survey below.

- The survey software will enable or disable some questions depending on your responses.
- Based on validation testing we estimate it will take no more than 10 minutes to complete the survey.
- Please answer all questions as accurately as possible.
- Although for brevity we use the terms 'ICU', 'intensive care' and 'critical care' interchangeably, please also consider in your responses all high-dependency beds for which your service is responsible.
- Patients with COVID-19 are defined as patients with a positive PCR test and organ failure requiring treatment.

BACKGROUND INFORMATION		
1	Which of the following answers most accurately describes your hospital?	
 
• District General Hospital
 
• Teaching Hospital
 
• Tertiary referral centre or University Hospital
 

2	What's the name of your trust and hospital?	
 
• Trust name:
 
• Hospital name:
 

3	How many staffed Intensive Care beds (level 2 and level 3) does your Department have (excluding any surge areas)?	
4	Was your capacity increased during COVID-19?	
 
• Yes (If yes, go to Q5)
 
• No
 

5	By what number of beds was your unit's capacity increased during COVID-19?	
6	Can you estimate the number of patients with COVID-19 admitted to your unit during the pandemic?	

FOLLOW-UP SERVICES		
7	Do you currently run an ICU follow-up clinic for patients with COVID-19?	
 
Yes (If yes, go to Q2)
 
No (If no, go to Q13)
 

8	Was the ICU follow-up clinic running prior to COVID-19?	
 
Yes (If yes, go to Q3)
 
No (If no, go to Q4)
 

9	Have any changes been made to the way your ICU clinic is run for COVID-19 patients?	
 
Yes (Please specify)
 
No
 

10	Have any changes been made to the way you run ICU clinics for non-COVID-19 patients?	
 
Yes (Please specify)
 
No
 

11	If you had surge areas within your hospitals, where high flow oxygen/CPAP was provided but patients were cared for by medical teams, were these patients also invited to ICU follow-up clinic?	
 
Yes
 
No
 
Followed up by other specialties (Respiratory/ID)
 

12	How soon after hospital discharge do you contact patients?	
 
Within a week
 
Within 2 weeks
 
Within a month
 
Within 2 months
 
Within 3 months
 
Other (please specify)
 

13	In addition to the ICU follow-up service, are there any alternative arrangements for follow-up for COVID-19 patients?	
 
Yes:
 
Respiratory team led
 
GP led
 
ID led
 
Other (please specify)
 
No
 

14	Which MDT professionals are part of your ICU follow-up clinic? (Please select all that apply)	
 
ICU consultant
 
Critical Care Nurse / Specialist Nurse
 
Physiotherapist
 
Psychologist
 
Dietician
 
Respiratory physician
 
Infectious Diseases physician
 
Other (Please specify)
 

15	Which patients do you invite to attend the ICU follow-up clinic?	
 
All patients admitted to the ICU
 
All patients treated on the ICU for 24hrs or longer
 
All patients treated on the ICU for 3 or 4 days or longer
 
Other (Please specify)
 

16	At what time points do you invite patients to the clinic for their first visit?	
 
3 months post ICU or hospital discharge
 
6 months post ICU or hospital discharge
 
Other (please specify)
 

17	If patients are invited to attend more than one follow-up clinic, please indicate all relevant times:	
 
3 months post ICU or hospital discharge
 
6 months post ICU or hospital discharge
 
12 months post ICU or hospital discharge
 
Other (please specify)
 

18	What tools are used to determine a patients' functional recovery? (Please select all that apply)	
 
SF-36 (any version)
 
HADS
 
Locally derived questionnaire
 
EQ-5D
 

		
 
PTSD screening tool (please specify)
 
Others (please specify)
 

19	Does the clinic have pre-negotiated access to any of the following services (not simply referral letters), if they are not already integral to the ICU follow-up clinic? (Please select all that apply)	
 
Clinical psychologist
 
Occupational therapist
 
ENT
 
Physiotherapy
 
Urology/Sexual Health Medicine
 
Other (Please specify)
 

20	How is the follow-up clinic funded?	
 
Not funded
 
ICU budget
 
Primary Care Trust
 
Other (please specify)
 
Don't know
 

21	In your opinion, is there a reason for your ICU having no follow-up clinic? (Please select all that apply)	
 
Financial constraints
 
Lack of clinical need
 
Lack of current evidence of benefit
 
Other (please specify)
 
No
 

22	Please feel free to add any additional comments here:	

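### Appendix 8: three of the five printed jumps in the follow-up-services survey point to the wrong item, and no skip separates units with a clinic from units without one (minor).

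*Combined protocol and SAP*

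**What the plan says.** Exploratory objective 4 (section 3.2) concerns regional variation in what follow-up is available to survivors and how it is organised. Section 5.2 describes an online survey offered to all UK intensive care units, and section 5.3 places its questions in Appendix 8.

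The form runs from Q1 to Q22. Q1-Q6 are background and Q7 onward concern follow-up services. Five jumps are printed:

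- Q4 (capacity increased) Yes goes to Q5.
- Q7 (clinic for COVID-19 patients) Yes: "Yes (If yes, go to Q2".
- Q7 No: "No (If no, go to Q13".
- Q8 (clinic running before COVID-19) Yes: "Yes (If yes, go to Q3".
- Q8 No: "No (If no, go to Q4".

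No jump is printed after Q13 or after Q20. The instructions add: "The survey software will enable or disable some questions depending on your responses". They do not give the programmed logic.

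**The concern.** Three of the jumps land in the background block. Q2 reads "What's the name of your trust and hospital", Q3 asks for staffed beds and Q4 asks whether capacity was increased. None is a sensible next step for a unit that has just described its clinic.

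Units without a clinic have a different problem. Q13, on other follow-up arrangements, is a reasonable place to send them, although its wording assumes an ICU service exists. The next item is Q14, "Which MDT professionals are part of your ICU follow-up clinic", and the clinic questions continue to Q20. Only then comes the item meant for these units, Q21: "In your opinion, is there a reason for your ICU having no follow-up clinic". Clinic units have no printed route past Q21.

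This matters because the survey is the only unit-level source for how services are structured. The clinic items print no not-applicable option. At Q20, a unit without a clinic could choose the answer for no funding and look like a unit running an unfunded clinic. At Q21, a clinic unit could answer No and look like a unit that has no clinic and no reason to give.

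**Working it through.** No sample-size or power figure is involved. The check is to trace the form, taking the next item in sequence wherever no jump is printed.

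**Inputs (Appendix 8).** Background items: Q1-Q6, so 6. Printed targets: Q4 Yes to 5; Q7 Yes to 2; Q7 No to 13; Q8 Yes to 3; Q8 No to 4.

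**Possible source of the error.** If the follow-up block had once been numbered from 1, each target would need the 6 background items added: 2 + 6 = 8, 3 + 6 = 9, 4 + 6 = 10. These are workable targets, so leftover section-level numbering is the likely explanation, though it is an inference. The same shift applied to Q7 No gives 13 + 6 = 19, which is not workable. The printed Q13 is the better target, so one offset does not repair every jump.

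**Routes under three readings.**

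| Reading | Unit with a clinic | Unit without a clinic |
|---|---|---|
| Targets as printed | 1-7, back to 2, round to 7 again; never reaches Q8-Q22 | 1-7, then 13-22; meets Q14-Q20 before Q21 |
| All Q7-Q8 targets + 6 | Q8 Yes: 1-22. Q8 No: 1-8, then 10-22. Both are shown Q21 | 1-7, then 19-22; misses Q13, meets Q19-Q20 before Q21 |
| Q7 Yes and both Q8 targets + 6, Q13 as printed | As in the row above; shown Q21 | 1-7, then 13-22; meets Q14-Q20 before Q21 |

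No reading routes units without a clinic correctly. Renumbering repairs the route into the clinic items but not the missing skips.

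**Counts.** Wrong jumps: 3 of 5 (Q7 Yes, Q8 Yes, Q8 No). Items between Q13 and Q21: 20 - 14 + 1 = 7. Q18, on tools for assessing functional recovery, does not name the clinic, so the safe count of clinic-only items is at least 7 - 1 = 6 (Q14-Q17, Q19, Q20). Missing skips: 2 (from Q13 to Q21 for units without a clinic; from Q20 past Q21 for units with one).

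**The case against.** The strongest reply is that respondents do not follow printed arrows. The survey is online, and the instructions say that software controls which items are active. They do not say that it uses the printed item numbers, and switching items on or off is not the same as jumping backwards. The instructions also cite validation testing for a completion time of at most 10 minutes, which would be hard to obtain from a form that loops for every clinic unit. Nor does the printed form list every branch: Q4 No has no printed skip past Q5, which only makes sense after a Yes. The missing skips after Q13 and Q20 may likewise exist in the software.

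The harm is also bounded. Hospital name (Q2) and clinic availability (Q7) are answered before any faulty jump. Spurious clinic answers can be filtered on Q7. The interview guide (Appendix 7) also asks patients about the follow-up they were offered, so the survey is not the only source on services.

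Most of this stands as a limit on the consequence. A reader might infer that the objective 4 data are corrupted, or that every clinic unit was misrouted. The documents do not support either, because the programmed branching is not in them.

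It does not remove the fault. The printed rules are the only routing the protocol gives. If the software follows them it inherits the errors; if it does not, the appendix misdescribes the instrument. The validation testing is cited only for duration. Filtering on Q7 cannot restore answers that were never requested or that were lost when a respondent gave up.

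**Conclusion.** The point holds as a minor fault in the data-collection form. Three of five printed jumps do not match the 1-22 numbering. Units without a clinic meet at least six clinic-only items before the one meant for them, and clinic units are not steered past Q21.

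The consequence is conditional. If the survey was built from the printed rules, clinic units loop back before the items on service structure, and units without a clinic may give spurious answers or drop out before Q21. The number of units affected cannot be estimated, because the documents give neither the number of units invited nor the programmed logic.

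The part at risk is the structure of services. Availability by hospital is not affected, on the assumption that partly completed responses are kept. Objective 4 is exploratory in section 3.2 (listed as secondary in the study summary) and is measured on units, so the patient-level primary outcome is untouched. Treating Q7 No as having no clinic is a further assumption, since Q7 asks only about a clinic for COVID-19 patients.

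**What to change.** In Appendix 8:

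- Set Q7 Yes to Q8 and Q8 Yes to Q9.
- Have the sponsor confirm the target of Q8 No. The offset gives Q10, but Q10 asks about changes to clinics for patients without COVID-19 and may itself presuppose an earlier clinic.
- Keep Q7 No to Q13, and add a skip from Q13 to Q21 for units without a clinic.
- Send clinic units from Q20 to Q22.

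Then check the programmed branching against the corrected form before analysis. In the analysis, restrict Q14-Q20 to units answering Yes at Q7 and Q21 to units answering No.

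The cost is a few edits to the form and, if the software shares the faults, to its logic. If responses already collected were misrouted, the restriction on Q7 removes spurious answers, but answers never requested could be recovered only by contacting the units again.

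### Follow-up services survey, Q11: no answer for hospitals without a medical-team surge area and no earlier item that identifies them, so its shares have no clean denominator

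*Combined protocol and SAP*

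**What the plan says.** Exploratory objective 4 (section 3.2) concerns geographical differences in the follow-up services available after critical COVID-19. Section 5.2 invites all UK intensive care units to complete the online survey printed in Appendix 8.

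Q11 of that survey opens "If you had surge areas within your hospitals, where high flow oxygen/CPAP was provided but patients were cared for by medical teams" and asks whether those patients were also invited to the ICU follow-up clinic. Three answers are printed: *Yes*, *No*, and "Followed up by other specialties (Respiratory/ID)". There is no not-applicable, other or don't-know answer.

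The survey instructions state "The survey software will enable or disable some questions depending on your responses". They also state "Please answer all questions as accurately as possible".

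The earlier items nearest to the subject are:

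- Q3, a count of staffed beds, "excluding any surge areas".
- Q4, "Was your capacity increased during COVID-19", with *Yes* leading to Q5.
- Q5, "By what number of beds was your unit's capacity increased during COVID-19".
- Q7, whether the unit runs an ICU follow-up clinic for COVID-19 patients, with the route "No (If no, go to Q13)".

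**The concern.** A clinic-running unit whose hospital had no surge area under medical teams reaches Q11 and finds no truthful answer. It can tick *No*, which reads as a decision not to invite patients who did not exist, or leave the item blank, which reads as non-response. In either case the analyst cannot tell from the form which units belong in the denominator.

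At stake is how one descriptive item can be interpreted: whether patients given respiratory support outside the ICU were offered the ICU clinic. The share answering *No*, or *Yes*, cannot be read as a rate among hospitals that had such patients.

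There is a second, smaller fault. *No* and the other-specialty answer can both be true of one unit, because patients followed up by respiratory or infectious-disease teams may not have been invited to the ICU clinic either. Q11 is not marked as multiple choice, whereas Q14, Q18, Q19 and Q21 are.

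**Working it through.** **1. Can branching screen Q11 out?** Branching needs an earlier response that carries the information. The candidates are:

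| Item | What it records | Shows whether a medical-team surge area existed? |
|---|---|---|
| Q3 | Staffed level 2 and 3 beds, surge areas left out | No |
| Q4 | Whether capacity rose | No: a unit could answer *No* and still have a CPAP ward run by physicians, or *Yes* and have none |
| Q5 | How many beds the unit itself added | No |
| Q6 | Estimated COVID-19 admissions to the unit | No |
| Q7 | Whether a COVID-19 follow-up clinic runs | No: it screens on having a clinic |
| Q8 to Q10 | History of the clinic and changes to it | No |

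The only written route past Q11 is Q7 = *No*. Some routing numbers at Q7 and Q8 appear to count from the start of that block rather than from Q1. On that count the target of Q7 = *No* would be Q19 instead of Q13, which also lies beyond Q11. Q11 therefore reaches clinic-running units only, with or without a surge area.

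**2. Do later items recover the information?** Q13 asks about alternative follow-up for COVID-19 patients in general, not surge-area patients. Q22 is open free text. Neither identifies the units that had no such area.

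**3. How far could the *No* share move?** The plan gives no figure to reproduce, and every value here is assumed. Let

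- s = share of clinic-running units with no such area;
- q = share answering *No* among units that had one (0.40);
- b = share of the units without an area that leave Q11 blank, the rest ticking *No*.

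Observed *No* among those answering = [s(1 − b) + (1 − s)q] / (1 − sb).

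With s = 0.30:

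- b = 0: 0.30 + 0.70 × 0.40 = 0.58, or 58%.
- b = 0.5: (0.15 + 0.28) / 0.85 = 0.43 / 0.85 = 0.506, about 51%.
- b = 1: 0.28 / 0.70 = 0.40, or 40%.

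Varying s with b = 0:

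- s = 0.10: 0.10 + 0.90 × 0.40 = 0.46, or 46%.
- s = 0.50: 0.50 + 0.50 × 0.40 = 0.70, or 70%.

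The b = 0 results are upper bounds for the assumed s and q. At b = 1 the share among answers is right, but the analyst could not know it, since blanks for no such area look the same as blanks for non-response.

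**The case against.** The strongest reply is that Q11 is worded conditionally, so a unit without such an area may simply skip it, and nothing in Appendix 8 makes the item mandatory. The request to answer everything is general and stands beside the statement that some questions will be disabled. Q17 also has a conditional stem and no not-applicable answer, so this is a habit of the form. This stands to the extent that mixing under *No* is likely rather than certain. It does not rescue the denominator, because a blank is no easier to interpret.

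A reader might infer more than the documents support in two ways:

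- **That the item will produce a spurious regional difference.** With q = 0.40 and every unit without an area ticking *No*, regions with s = 0.10 and s = 0.50 would differ by 70% − 46% = 24 points. But no regional analysis of Q11 is stated, and nothing in the documents supports those values of s or such regional variation.
- **That a *No* means patients were left without follow-up.** Q11 asks only about invitation to the ICU clinic. Q13 covers other follow-up arrangements for COVID-19 patients, though not specifically for surge-area patients.

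It is also fair to say that Q2 records trust and hospital, so unclear answers can be queried, and that the survey is mainly about care provided by ICUs to their own patients. Both points lower the importance of the fault without removing it.

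**Conclusion.** The point holds in a limited form. Q11 offers no answer to a clinic-running unit whose hospital had no medical-team surge area, and no earlier item identifies such units. Its *No* may mix two different situations, a blank is ambiguous in the same way, and the Q11 shares therefore lack a clean denominator for exploratory objective 4.

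The size is unknown. Under the assumed 40% and 30%, the observed *No* lies between 40% and 58%, depending on how many units without an area leave the item blank. The range rests on those two values and on the units without an area either ticking *No* or leaving the item blank. The finding is minor and does not touch the primary outcome.

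**What to change.** Add an answer to Q11 such as *Not applicable: no such area in our hospital*, and report Q11 only among units that had such an area. If the survey has already launched, report it only for units confirmed to have had one, using the hospital name from Q2 to query unclear answers.

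If the overlap between answers is also to be removed, replace the last two options with *Not invited to ICU clinic, followed up by another service* and *Not invited to ICU clinic, no other follow-up or not known*. Do not turn *No* into a statement that no other follow-up was arranged. That would leave no option for GP-led or unknown follow-up and would ask ICU staff to vouch for care given by other teams.

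The cost before launch is one added option, and optionally two relabelled ones, in an online form, plus whatever section 7.7 requires for a change to a protocol appendix. After launch it is some queries to sites and a smaller denominator for this item. The team's own Appendix 9 already does this: its Q19 screens respondents before Q20, and its Q21 has a not-applicable column.
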